8.6 Pregnancy

Medical Monitor

SAE Email: [REDACTED]

24-hour telephone: [REDACTED]

If a female subject becomes pregnant during the treatment period or within 6 months after the last study medication application, a Pregnancy Report form should be completed. While not an AE or SAE the investigator must submit the completed Pregnancy Report form to the Medical Monitor within 24 hours of learning of the pregnancy.

Abortion, whether therapeutic or spontaneous, will also be reported on a Pregnancy Report form and sent to the Medical Monitor. If the abortion meets seriousness criteria, this information will be captured on the AE CRF and SAE form.

Any congenital anomaly/birth defect in a child born to a female subject should be recorded and reported as an SAE.

8.6.1 Woman of Childbearing Potential (WOCBP)

WOCBP includes any female who has experienced menarche and who has not undergone successful surgical sterilization (e.g., hysterectomy, bilateral tubal ligation, bilateral occlusion of the fallopian tubes or bilateral oophorectomy) or is not postmenopausal. Postmenopausal is defined as ≥ 12 months with no menses without an alternative medical cause. WOCBP must have a negative UPT at Visit 1 to be enrolled in the study and at Visit 2 to be randomized to study medication.

8.6.2 Protocol approved methods of birth control

The investigator will discuss the potential risk factors associated with pregnancy and the importance of maintaining a highly effective method of birth control with all WOCBP. All WOCBP must use a protocol approved method of birth control throughout the duration of the study and for 30 days after the last study medication application.

For this study protocol approved methods of birth control include:

- Women who are abstinent from reproductive sex as a matter of lifestyle (*i.e.*, women having sex with women); or who are abstinent are acceptable methods of contraception (as these methods, if followed consistently, are at least as effective as hormonal birth control pills)
- Women who are in a monogamous relationship with a partner who has a vasectomy
- Combined (estrogen and progestogen containing) hormonal contraception associated with inhibition of ovulation:
 - Oral
 - Transdermal
 - Intravaginal
- Progestogen-only hormonal contraception associated with inhibition of ovulation:
 - Oral
 - Implantable
 - Injectable
- Intrauterine device (IUD)
- Intrauterine hormone-releasing system
- Vaginal gel
- Double-barrier methods (*e.g.*, condoms with spermicide, diaphragm/cervical cap with spermicide).

WOCBP must be on at least 1 protocol approved method of birth control for the following time periods prior to Visit 1:

- Abstinence (≥ 30 days)
- Partner with vasectomy (≥ 30 days)
- Vaginal gels (≥ 30 days)
- Implants (on a stable dose for ≥ 30 days)
- Injectables (on a stable dose for ≥ 30 days)
- Patches (on a stable dose for ≥ 30 days)
- Combined oral contraceptives (on a stable dose for ≥ 30 days)
- Intrauterine devices (inserted for ≥ 30 days).

Prior to trial enrollment the investigator must discuss with all WOCBP the potential risk factors associated with a pregnancy during the study and the importance of avoiding pregnancy during study participation. The subject must sign an informed consent form documenting this discussion. During the trial, all WOCBP will be instructed to contact the investigator immediately if they suspect they might be pregnant (*e.g.*, missed or late menstrual period).

If a subject or investigator suspects that the subject may be pregnant prior to study medication administration, the study medication must be withheld until the results of a pregnancy test are

available. If pregnancy is confirmed, the subject must not receive study medication and must be discharged from the study.

If, following the first study medication application it is determined that the subject may have been or was pregnant at the time of study medication exposure (including 30 days after the last study medication application) the investigator must immediately notify the Medical Monitor and record the pregnancy on a pregnancy surveillance form. While not an AE or SAE, the investigator must report every pregnancy using a pregnancy surveillance form and follow the same reporting procedures as described for reporting an SAE.

Protocol-required procedures for trial discontinuation and follow-up must be performed on the subject unless contraindicated by pregnancy (*e.g.*, x-ray studies). Other appropriate pregnancy follow-up procedures should be considered if indicated. In addition, the investigator must report follow-up information regarding the course of the pregnancy, including perinatal and neonatal outcome on the pregnancy surveillance form. Infants should be followed for a minimum of six weeks.

9 STATISTICAL METHODOLOGY

9.1 Sample Size Determination

This is a Phase 2b study designed to evaluate the safety and efficacy of two doses of NFX-179 Gel in comparison to Vehicle Gel. Approximately 168 subjects with cNF are planned to be randomized in the study. The sample size has been chosen to assure at least 150 randomized subjects complete the study. It is based on the assumption that the proportion of responders will be approximately [REDACTED] in the vehicle treated group and at least [REDACTED] in the most effective active treated group. Alpha two-tail is 0.05. Under these assumptions power is expected to be at least 90% given the planned sample size.

9.2 Randomization

Subjects will be randomized with a treatment allocation ratio of 1:1:1 (NFX-179 Gel [REDACTED] to NFX-179 Gel [REDACTED] to Vehicle Gel).

9.3 Statistical Analyses

9.3.1 General Approach

All randomized and treated subjects will be assessed in analyses of safety and efficacy. Descriptive statistics will be produced on relevant screening and baseline data and on demographic characteristics. Safety and efficacy endpoints will be summarized descriptively by treatment (when applicable) and for all subjects combined and may be analyzed using appropriate parametric or nonparametric inference tests. Comparisons between NFX-179 treated cNFs and vehicle treated cNFs will also be performed as described below. Summaries and analyses will be based primarily on non-missing data.

9.3.2 Analysis Populations and Missing-Data Imputation

All subjects who are randomized and dispensed study drug and have at least one post-baseline visit with efficacy evaluations will be included in the intent-to-treat (ITT) population.

Missing data imputation procedures based on the ITT population are described below. The Observed Cases (OC) population will include all subjects in the ITT population with observed efficacy data at Visit 8. No data imputation will be used with this population for subjects with missing data at any post-baseline visit.

The Observed Cases (OC) population will be used for primary and secondary efficacy analyses to address the main efficacy evaluation objective of the study. There will also be two sensitivity analyses of efficacy. For the first sensitivity analyses, the Per-Protocol (PP) population, drawn from the OC population subjects who completed the study through Visit 8 with no major protocol violations, will be used. For the second sensitivity analyses, the ITT population will be used, and all missing post-baseline efficacy data will be imputed using last observation carried forward (LOCF) from the last available observed efficacy data after the Baseline visit. Mixed Model-based missing data imputation or Multiple Imputation may be used as a supplementary imputation method. A supplemental efficacy analysis based specifically on subject Responders will also be conducted using the ITT population where subjects terminating the study before completing Visit 8 due to treatment-related adverse events will be imputed as Non-Responders. All efficacy analyses will perform separate

comparisons of each Active treatment group with the Vehicle group along with other contrasts described below. No adjustments for multiplicity will be made. All subjects who are randomized, received at least one confirmed dose of study drug, and have at least one post-baseline safety evaluation will be included in the Safety Population.

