5.4.3 Early Termination Visit

The investigator should complete the following study procedures for randomized subjects who prematurely discontinue from the study:

- For subjects who discontinue from the study prior to Visit 8, complete the Visit 8 procedures
- For subjects who complete Visit 8 and discontinue from the study prior to Visit 9 complete the Visit 9 procedures.

Detailed instructions for documenting subjects who prematurely discontinue from the study will be included in the CRF completion guidelines.

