6.2.3 Visit 3/Day 8/Week 1: 7(± 4 days) after Visit 2 (QD treatment)

Subjects should not apply the study medication within 6 hours prior to these visits.

At Visit 3, the investigator or designee will perform the following procedures:

1. Query the subject in a non-directive manner about any changes in her/his health since the previous visit and report all AEs as appropriate
2. Query the subject about any changes in her/his concomitant therapies since the previous visit and report changes as appropriate
3. Confirm the subject has followed all study instructions
4. Confirm the location of each Target cNF
5. Have the subject perform an LTA of the symptoms for each Target cNF
6. The investigator will perform an LTA of the signs for each Target cNF
7. Weigh study medication
8. Collect and dispense study medication as appropriate
9. Review the study instructions, including application technique and Target cNF locations, with the subject
10. Schedule the next study visit.
11. Remind subject to apply study medication 4 (\pm 2) hours prior to Visit 4

6.2.4 Visit 4/Day 29/Week 4: 28 (\pm 4 days) after Visit 2 (QD treatment)

Only at select sites participating in Pharmacokinetic sampling: At Visit 4, subjects must apply the study medication 4 (\pm 2) hours prior to this visit.

At sites NOT participating in Pharmacokinetic sampling: At Visit 4, subjects should not apply the study medication within 6 hours prior to this visit.

At Visit 4, the investigator or designee will perform the following procedures:

1. Query the subject in a non-directive manner about any changes in her/his health since the previous visit and report all AEs as appropriate
2. Query the subject about any changes in her/his concomitant therapies since the previous visit and report changes as appropriate
3. Confirm the subject has followed all study instructions
4. Collect samples for clinical laboratory tests and pharmacokinetics
5. Record date and time of last study medication application
6. Record 24-hour time of pharmacokinetic sample collection
7. Perform a urine pregnancy test for WOCBP
8. Confirm the location of each Target cNF
9. **FOR EACH TARGET cNF:**
 - Perform a PTA
 - Have the subject perform an SSA
 - Measure the dimensions
10. Have the subject perform an LTA of the symptoms for each Target cNF
11. The investigator will perform an LTA of the signs for each Target cNF
12. Weigh study medication
13. Collect and dispense study medication as appropriate

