13. Measure the dimensions of each Target cNF
14. Take standardized photographs of each Target cNF
15. Weigh study medication
16. Collect all study medication
17. Review the study instructions with the subject. If the subject wishes to be contacted about participation in the exit interview study inform the identified individual at the exit interview vendor that the subject has completed study participation and provide them with the subject's contact information
18. Schedule the next study visit.

6.2.9 Visit 9/Day 211/Week 30 (End of study, early termination if subject completes Visit 8 and discontinues from the study prior to Visit 9)

This visit must occur 210 days (± 4 days) after Visit 2.

At this visit, the investigator or designee will perform the following procedures:

1. Query the subject in a non-directive manner about any changes in her/his health since the previous visit and report all AEs as appropriate
2. Query the subject about any changes in her/his concomitant therapies since the previous visit and report changes as appropriate
3. Confirm the subject has followed all study instructions
4. Measure vital signs
5. Perform a urine pregnancy test for WOCBP
6. Confirm the location of each Target cNF
7. Have the subject perform an LTA of the symptoms for each Target cNF
8. The investigator will perform an LTA of the signs for each Target cNF
9. Measure the dimensions of each Target cNF
10. Take standardized photographs of each Target cNF
11. Perform a PTA for each Target cNF
12. Have the subject perform a SSA for each Target cNF
13. Discharge the subject from the study.

6.2.10 *Unscheduled Visit*

The investigator may see a subject for an unscheduled study visit at any time it is necessary, in the investigator's opinion.

At unscheduled visits, the investigator or designee will perform the following procedures, at a minimum:

1. Query the subject in a non-directive manner about any changes in her/his health since the previous visit and report all AEs as appropriate
2. Query the subject about any changes in her/his concomitant therapies since the previous visit and report changes as appropriate
3. Review the study instructions with the subject
4. Schedule the next study visit.

Complete other study procedures that are, in the investigator's opinion, appropriate for the visit. Detailed instructions for documenting unscheduled visits will be included in the CRF completion guidelines.

6.3 **Target cNF identification**

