7.2.1 Target cNF dimensions

At Visits 1, 2 (prior to the first study medication application), 4, 5, 6, 7, 8 and 9 the investigator will measure the length, width, and height above surrounding skin, in millimeters (mm) of each Target cNF using the ruler provided by NFlection Therapeutics, Inc.

At Visits 1 and 2, to be enrolled in the study a subject's Target cNFs located on the face must each have a length $\geq 5\text{mm}$ and $\leq 14\text{mm}$, a width $\geq 5\text{mm}$ and $\leq 14\text{mm}$ and a height $\geq 2\text{mm}$. Target cNFs located on the anterior trunk or upper extremities must each have a length of $\geq 7\text{mm}$ and $\leq 14\text{mm}$, a width of $\geq 5\text{mm}$ and $\leq 14\text{mm}$ and a height of $\geq 2\text{mm}$.

The investigator must report the following dimensions to the nearest 0.5mm using the half-millimeter graduated side of the ruler:

1. Determine if a clinically visible cNF tumor meets the inclusion criteria of the study protocol.

The identified area of the skin should be examined with a suitable examination light and may be used to determine whether the cNF tumor meets the inclusion criteria. No magnification can be used. Once it has been determined that a qualifying cNF tumor is present, measure the height, length, and width using the procedure described below:

2. Measure the height of the cNF tumor.

The cNF tumor should be examined with a suitable examination light. Cross lighting (tangential to cNF) may be used. Magnification may NOT be used.

[figure not shown]
The height of the cNF tumor should be measured at its highest point above the surrounding non-tumor skin. Use the ruler provided as illustrated below. The ruler should be gently placed on the non-tumor skin directly behind the cNF, perpendicular to the skin without creating a depression on the skin. Examine the visible cNF on a line parallel with the plane of the surrounding non-tumor skin and observe the ruler marking

at the highest point of the lesion. Report the cNF height to the nearest 0.5 mm using the half-millimeter graduated side of the scale.

As a guideline report the cNF tumor height as:

- **0mm:** define 0.5mm as the limit of detectability, therefore any cNF tumor <0.5mm will be rated as 0mm
- **0.5mm:** define 0.5mm as any cNF tumor that is $\geq 0.5\text{mm}$ and $< 1.0\text{mm}$
- **1.0mm:** define 1.0mm as any cNF tumor that is $\geq 1.0\text{mm}$ and $< 1.5\text{mm}$

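### The set called ITT requires a post-baseline efficacy visit, so an early treatment-related dropout without one is missing even from the analysis that scores such dropouts as Non-Responders

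*Combined protocol and SAP*

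**What the plan says.** All references are to the combined protocol and SAP. Section 9.3.2, repeated in the Synopsis under Statistical Methods, defines the sets and their uses:

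- **ITT.** Subjects who are randomized, are dispensed drug and "have at least one post-baseline visit with efficacy evaluations will be included in the intent-to-treat (ITT) population".
- **Observed Cases (OC).** ITT subjects with efficacy data at Visit 8, without imputation. This set carries the primary and secondary analyses. Per-Protocol, the first sensitivity analysis, is drawn from OC.
- **Second sensitivity analysis.** Run on ITT, with missing values "imputed using last observation carried forward (LOCF) from the last available observed efficacy data after the Baseline visit".
- **Supplemental subject-responder analysis.** Also run on ITT; here "subjects terminating the study before completing Visit 8 due to treatment-related adverse events will be imputed as Non-Responders".

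Section 9.3.1 makes a broader statement: "All randomized and treated subjects will be assessed in analyses of safety and efficacy".

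On timing, 7.2.1 says "At Visits 1, 2 (prior to the first study medication application), 4, 5, 6, 7, 8 and 9 the investigator will measure" the tumors, so Visit 3 is not included. The next visit is headed "Visit 4/Day 29/Week 4" (6.2.4). For early leavers, 5.4.3 says: "For subjects who discontinue from the study prior to Visit 8, complete the Visit 8 procedures". Those procedures (6.2.8) include "Measure the dimensions of each Target cNF" as well as the physician and subject assessments.

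**The concern.** Membership of a set labelled intent-to-treat depends here on something observed after randomization. That matters most for the supplemental responder analysis, which is the only committed analysis that treats stopping for a treatment-related event as failure. A subject who stops in the second week for such an event and is not seen again for efficacy would normally be in the Safety Population, because tolerability is scored within about 20 minutes of the first application. The same subject would appear in neither the numerator nor the denominator of the responder rate. If such losses were more common on active gel than on vehicle, the active responder rate in this analysis would be somewhat too high, and no other committed analysis would show it.

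**Working it through.** **1. First scheduled post-baseline efficacy reading.** The Visit 3 list (6.2.3, Day 8) covers adverse events, concomitant therapy, local tolerability and tube weight. It has no dimensions, PTA or SSA, and 7.2.1, 7.2.2 and 7.2.3 all omit Visit 3. Visit 4 is 28 ± 4 days after Visit 2, that is Day 29 with a window of Days 25 to 33.

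**2. Who is excluded.** Take a subject who stops before Visit 4 for a treatment-related event:

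| What happens next | Post-baseline efficacy reading | In ITT and in the Non-Responder analysis |
|---|---|---|
| Attends the early termination visit (5.4.3, 6.2.8) | Yes | Yes |
| Has an unscheduled visit with efficacy added (6.2.10, optional) | Yes | Yes |
| Neither (lost to follow-up, declines, misses the visit) | No | No |

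Only the last row is affected.

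**3. Whether another analysis recovers that row.** OC and Per-Protocol require Visit 8 data, so they do not. LOCF is run on ITT and carries only values obtained after Baseline, so there is nothing to carry. Mixed-model or multiple imputation is optional and is not tied to a wider set.

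**4. Numbers available.** 168 randomized at 1:1:1 gives 168/3 = 56 per arm. 150 completing gives 150/3 = 50 per arm. The implied loss is 18/168 = 10.7%, or 6 per arm over the whole study. The stated power of at least 90% (9.1) cannot be reproduced, because both responder proportions are redacted. The response rates below are therefore assumptions.

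**5. Size.** Let k of 56 active subjects fall in the excluded row, and let p be the responder rate among the other 56 − k, with no other losses. The plan reports p. Counting the k subjects as Non-Responders gives p(56 − k)/56, so the difference is p·k/56.

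| Assumed p | k = 1 | k = 3 | k = 6 |
|---|---|---|---|
| 30% | 0.5 points | 1.6 points | 3.2 points |
| 40% | 0.7 points | 2.1 points | 4.3 points |
| 50% | 0.9 points | 2.7 points | 5.4 points |

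For example, 0.40 × 55/56 = 39.3%, which is 0.7 points below 40%. With k = 0 nothing changes. Similar losses on vehicle would partly offset the effect on the treatment difference.

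**6. Mapping of the termination visit.** Section 6.2.8 names Visit 8 as the early termination visit, yet requires it 182 ± 4 days after Visit 2 (Days 179 to 187). OC turns on Visit 8 data, and no rule says whether a termination reading qualifies. If it does, a reading at about Day 10 could enter the primary analysis as a 182-day outcome. The Non-Responder rule is also affected, because it applies to subjects who stop before completing Visit 8.

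**The case against.** The strongest reply is that the plan already provides for early leavers: 5.4.3 asks for full Visit 8 procedures from anyone who stops before Visit 8. A reader might infer from the ITT definition that all early dropouts disappear. The documents do not support that, because those who attend the termination visit stay in ITT and, if they stopped for a treatment-related event, are scored as Non-Responders.

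Second, the number affected may be very small. The 28-day study (2.2.2) reported no treatment-related TEAEs in 48 subjects. Section 5.6.9 allows reduced frequency or fewer treated tumors, with all 10 still evaluated, so intolerance need not mean leaving. This stands, but it does not establish zero. If 36 of the 48 were on active gel (an assumption: four equal groups), no events in 36 gives an upper 95% bound of 1 − 0.05^(1/36) = 8.0%, or about 4.5 of 56.

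Third, 9.3.1 is an introductory statement, and the same paragraph says analyses rest primarily on non-missing data. The conflict with 9.3.2 is real but would be minor without its effect on the Non-Responder analysis.

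A reader might also infer that LOCF favors active gel, or that multiple imputation should replace it. Neither follows. LOCF is only the second sensitivity analysis. If response builds over 182 days, carrying forward a partial-course reading may understate active gel. Multiple imputation from Visits 4 to 7 would have no post-baseline data for subjects who leave before Visit 4, so it would not cure this gap.

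**Conclusion.** The point holds in a narrow form. The set called ITT is a modified ITT. A treatment-related dropout with no post-baseline efficacy reading is missing from the one analysis designed to count that subject as a failure, and no other committed analysis restores the subject.

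The size is about 0.7 points of active responder rate per subject at an assumed 40% response (0.5 at 30%, 0.9 at 50%). The number of such subjects is not given and may be zero. The k = 6 column should not be read as an expected effect: it puts the whole implied per-arm loss before Visit 4, makes every case treatment-related with no efficacy reading, and assumes no such loss on vehicle. The primary analysis would be unchanged by a wider ITT definition, because OC would still require Visit 8 data. It does depend on how termination readings are mapped. The change is worth making because it is cheap and removes an avoidable bias, not because a large effect has been shown.

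**What to change.** Make three changes to 9.3.2 and the matching Synopsis text, before unblinding:

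1. Define ITT as all randomized subjects, analyzed by assigned arm, and align 9.3.1 with it.
2. In the supplemental responder analysis, count as Non-Responders all randomized subjects who stop before Visit 8 for a treatment-related adverse event, whether or not they have a post-baseline efficacy visit.
3. State that an early termination reading does not count as Visit 8 (Day 182) data for Observed Cases unless it falls in the Visit 8 window. For the Non-Responder rule, state that attending a termination visit outside that window does not count as completing Visit 8.

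The cost is SAP wording and minor programming, with no new data collection. The downside is that reported response rates may be slightly less favorable.
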